
Section 9.2: Clarified that subjects will be required to fast 2 hours prior to pharmacodynamic assessments.

Synopsis and Section 9.3.1: Revised inclusion criteria number 4 to reflect that the tumor sample is collected up to 8 weeks before administration of study drug.

Synopsis and Section 9.3.1: Revised inclusion criteria number 7, Part 2, Dose Expansion, to indicate that the fresh tumor tissue must be available and collected up to 8 weeks before administration of H3B-6527 on Cycle 1 Day 1.

Synopsis and Section 9.3.1: Revised inclusion criteria number 14 to define sexual abstinence in accordance with the Clinical Trial Facilitation Group guidance.

Synopsis and Section 9.3.2: Revised exclusion criteria number 9 to include the mention of the P-glycoprotein transporter.

Synopsis and Section 9.3.2: Revised exclusion criteria number 16 to replace corrected QT (QTc) >500 ms with QTc >450 ms, as >500 ms is considered a Grade 3 QTc prolongation as per Common Terminology Criteria for Adverse Events (CTCAE).

Synopsis and Section 9.3.2: Added exclusion criteria number 27, “Hereditary problems of galactose intolerance, the Lapp lactase deficiency, or glucose galactose malabsorption.”

Section 9.4.6: Revised to indicate that subjects will be instructed to take the dose in conjunction with a meal.

Synopsis and Section 9.4.8.1: Revised the list of prohibited concomitant therapy and procedures to include P-glycoprotein transporter

Section 9.5.1: Revised to indicate that all subjects must provide written informed consent up to 8 weeks before the first dose of study drug.
Section 9.5.1.1.1: Revised to indicate that a fresh tumor biopsy, the signing of the ICF, and the collection of blood samples for pharmacodynamic analysis (same day as fresh tumor biopsy) will be required up to 8 weeks before administration of H3B-6527 on Cycle 1 (C1) Day 1, in order to enroll in the Dose Expansion Phase of the study. The 28-day Screening Period will begin when any of the remaining screening assessments are performed. The entire Pretreatment Phase must be completed within 8 weeks of study drug administration on C1 Day 1.
Synopsis and Section 9.5.1.2.1: Revised to indicate that a brain scan should be performed for all subjects as clinically indicated.

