11. Treatment with proton pump inhibitors that cannot be discontinued 3 days prior to the start of study drug and during the course of the study; antacids are permitted except for calcium carbonate antacids (eg, Tums[®]).
12. Use of other investigational drugs within 28 days or at least 5 half-lives (whichever is shorter) before study drug administration.
13. Previous treatment with a selective FGF19-FGFR4 targeted therapy.

14. Use of any live vaccines against infectious diseases (eg, influenza, varicella) within 4 weeks (28 days) of initiation of study therapy.
15. Presence of gastric or esophageal varices requiring active treatment.
16. A clinically significant electrocardiogram (ECG) abnormality, including a marked baseline prolonged QTc interval (eg, a repeated demonstration of a QTc interval >450 ms).
17. Significant cardiovascular impairment: history of congestive heart failure greater than New York Heart Association Class II, uncontrolled arterial hypertension, unstable angina, myocardial infarction, or stroke within 6 months of the first dose of study drug; or cardiac arrhythmia requiring medical treatment (including oral anticoagulation).
18. Any other major illness, medical condition, or concomitant medication that, in the Investigator's judgment, will substantially increase the risk associated with the subject's participation in this study or would compromise the subject's ability to safely complete the study.
19. Males who have not had a successful vasectomy (confirmed azoospermia) or they and their female partners do not meet the criteria above (ie, not of childbearing potential or practicing highly effective contraception throughout the study period or for 90 days after study drug discontinuation). No sperm donation is allowed during the study period or for 90 days after study drug discontinuation
20. Hypersensitivity to the study drug or to any of the excipients.
21. Intolerance or hypersensitivity to both CT and MRI contrast material that would preclude the ability to acquire the triphasic liver imaging required by the protocol.
22. Inorganic phosphorus > ULN for the institution. Note: Subjects may be on treatment for hyperphosphatemia, but the levels must be normal at screening to participate in this study. Subjects with high levels on screening may subsequently be treated and rescreened and, should they have stable levels for 2 weeks prior to study, may enter the study.

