Furthermore, the frequency of laboratory abnormalities by maximum postbaseline CTCAE grade will be tabulated by cycle and overall for selected laboratory parameters to include at least hemoglobin, white blood cell count, ANC, lymphocytes, platelet count, AST, ALT, bilirubin, creatinine, alkaline phosphatase, and electrolytes. Shift tables will also be produced for these parameters based on the baseline CTCAE grade and the maximum CTCAE grade overall and by cycle.

9.7.1.8.4 **VITAL SIGNS**

Changes in vital sign parameters (including systolic and diastolic BP, HR, RR, and temperature) and body weight will be summarized over time, and any abnormal values will be tabulated.

9.7.1.8.5 **ELECTROCARDIOGRAMS AND HOLTER MONITORING**

For all subjects, shift tables will present changes from baseline in ECG interpretation (categorized as normal; abnormal, not clinically significant; and abnormal, clinically significant) to end of treatment.

In addition, the number (percentage) of subjects with at least 1 postbaseline abnormal ECG result in QTcF during the treatment period will be summarized. Clinically abnormal ECG results in QTcF will be categorized as follows:

Absolute QTc interval prolongation:

- QTc interval >450 ms
- QTc interval >480 ms
- QTc interval >500 ms

Change from baseline in QTc interval:

- QTc interval increases from baseline >30 ms
- QTc interval increases from baseline >60 ms

All ECG abnormalities will be listed on a per-subject basis.

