#### 5.6.5 Electrocardiograms

Descriptive statistics for ECG parameters (i.e. QTcF, QTcB, QT, QRS, heart rate and waveforms) and changes from baseline will be summarized over time. Shift tables will present changes from baseline in ECG interpretation (categorized as normal; abnormal, not clinically significant; and abnormal, clinically significant) to end of treatment.

In addition, the number (percentage) of subjects with at least 1 post baseline abnormal ECG result in QTcF during the treatment period will be summarized. Clinically abnormal ECG results in QTcF will be categorized as follows:

Absolute QTc interval prolongation:

- QTc interval > 450 ms
- QTc interval > 480 ms
- QTc interval > 500 ms

Change from baseline in QTc interval:

- QTc interval increases from baseline > 30 ms
- QTc interval increases from baseline > 60 ms

Listings of ECG results, ECG abnormalities and Holter recordings will be provided.

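### The absolute QTcF counts ignore baseline, so the >450 ms row, and mainly for earlier enrollees the >480 ms row, can report stable prolongation present at entry as an on-treatment abnormality

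*SAP*

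**What the plan says.** **Counting rule.** SAP 5.6.5 states that "the number (percentage) of subjects with at least 1 post baseline abnormal ECG result in QTcF during the treatment period will be summarized". The absolute categories start at "QTc interval > 450 ms" and continue at 480 and 500 ms. Protocol 9.7.1.8.5 uses the same rule: "subjects with at least 1 postbaseline abnormal ECG result in QTcF during the treatment period will be summarized". Neither text restricts the absolute rows to subjects who were at or below the threshold before dosing.

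**Where baseline is used.** Section 5.6.5 has separate change rows, such as "QTc interval increases from baseline > 30 ms" and the corresponding row for 60 ms. It plans descriptive changes from baseline over time, and listings. It also has one shift analysis: "Shift tables will present changes from baseline in ECG interpretation". That table uses the overall reading (normal, abnormal not clinically significant, abnormal clinically significant) and goes to end of treatment. It does not use QTcF categories or the worst value. SAP section 8 defines baseline as the last non-missing measurement before first dose, but the absolute rows do not use it.

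**Entry.** Protocol 9.3.2, criterion 16, excludes a clinically significant ECG abnormality, with this example: "a marked baseline prolonged QTc interval (eg, a repeated demonstration of a QTc interval >450 ms" (the bracket closes there). It names no correction formula. Protocol 9.5.1.4.6 has screening and baseline ECGs taken singly unless triplicates are clinically indicated. The Amendment 08 entry in the protocol's amendment history (28 Aug 2019) records that criterion 16 was revised "to replace corrected QT (QTc) >500 ms with QTc >450 ms".

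**Population.** The Safety Analysis Set (SAP 5.2.1) is every dosed subject, whichever amendment applied at entry. SAP section 5 breaks Part 1 tables down by dose cohort and Part 2 tables by schedule.

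**The concern.** A subject with QTcF 470 ms before the first dose who stays at 470 ms has not changed, yet is counted in the >450 ms row. A reader of a table of post-baseline abnormalities during treatment will tend to take that row as prolongation that began on treatment. Changes in ECG parameters belong to the primary safety endpoint (SAP 5.1.1), and Part 1 cohorts have 3 to 6 subjects, so one such subject moves the percentage a long way.

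The plan handles the same issue better elsewhere. Laboratory grades get a baseline-by-maximum shift table (SAP 5.6.3) and ECOG status gets a baseline-to-worst shift (SAP 5.6.6). Protocol 9.5.1.4.1 makes a QTcF result an adverse event only if it is above 450 ms and has also risen by more than 60 ms. QTcF, which SAP 5.6 names as the primary QTc parameter, has no comparable categorical table.

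**Working it through.** The plan gives no expected QTcF count, so there is no figure to reproduce. The check has four steps.

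**1. Which rows can include pre-existing prolongation?** The amendment history is used only to identify the limit that earlier subjects faced, not as a contradiction of the current text.

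| Row | Before Amendment 08 (example limit >500 ms) | Current criterion 16 (repeated >450 ms) |
|---|---|---|
| >450 ms | baseline of 451-500 ms did not meet the limit | possible through an unrepeated value |
| >480 ms | baseline of 481-500 ms did not meet the limit | only through an unrepeated value |
| >500 ms | little room: above the limit itself | only through an unrepeated value |

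Because entry ECGs are single, a repeat is not routine. An investigator could still exclude a lower value as clinically significant, so the table shows what the limit allowed, not who entered.

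**2. Weight of one such subject.** In a group of n subjects, one subject contributes 1/n:
- n = 3 (initial Part 1 cohort): 1/3 = 33.3 points
- n = 6 (full Part 1 cohort): 1/6 = 16.7 points
- n = 40 (Part 2 arm): 1/40 = 2.5 points

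**3. Would a stable subject be counted?** Assume no drug effect, independent normal variation around a true value μ with within-subject SD σ, and k post-baseline ECGs. The probability that at least one value exceeds threshold T is 1 − [Φ((T − μ)/σ)]^k. The ranges σ = 6-15 ms and k = 3-21 are assumptions.
- μ = 455, T = 450: at σ = 15 and k = 3, Φ(−5/15) = 0.369 and 1 − 0.369³ = 0.95. Over the range, 0.95-1.00.
- μ = 465, T = 450: at σ = 15 and k = 3, Φ(−1) = 0.159 and 1 − 0.159³ = 0.996. Over the range, 0.996-1.00.
- μ = 485, T = 480: the same 5 ms margin as the first case, so 0.95-1.00.
- μ = 455, T = 500: 0-0.03.
- μ = 485, T = 500: 0.02 (σ = 6, k = 3) to 0.97 (σ = 15, k = 21).

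The same stable subject shows an increase of more than 60 ms over a single baseline value with probability of about 0-0.03. For more than 30 ms the range is about 0-0.46, the upper end needing σ = 15 and k = 21. The change rows would therefore seldom show a large increase for this subject, while the >450 ms row almost always counts them.

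**4. Illustration for an arm of 40.** Suppose a share p of subjects has baseline >450 ms and all of them exceed 450 ms again, and that 5% of the rest newly exceed it. The planned row reads p + (1 − p) × 0.05. All of these inputs are assumptions.

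| p | Planned row | Subjects counted (of 40) | Truly new | Row limited to baseline ≤450 ms |
|---|---|---|---|---|
| 5% | 0.05 + 0.95 × 0.05 = 9.8% | 3.9 | 1.9 | 5.0% |
| 10% | 0.10 + 0.90 × 0.05 = 14.5% | 5.8 | 1.8 | 5.0% |
| 20% | 0.20 + 0.80 × 0.05 = 24.0% | 9.6 | 1.6 | 5.0% |

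**The case against.** The strongest reply is that the section does use baseline. It plans change-from-baseline statistics, >30 and >60 ms increase rows, an interpretation shift table and listings. In a cohort of 3 to 6, the listing shows at once that a subject at 470 ms did not move. The absolute rows are labelled as absolute and post-baseline, not as new or drug-related, so they are literally true. Criterion 10 also bars QT-prolonging drugs in the 2 weeks before dosing. The table shells and programming rules are in separate documents and may already contain a suitable display.

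Much of this stands. The problem is one of reading a descriptive table, and a careful reader could rebuild the answer from the listings. What remains is that no specified table separates onset from persistence for QTcF categories.

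A reader might also infer three stronger things that the documents do not support:
- **That all three thresholds are equally affected.** They are not. Above 500 ms was already the exclusion example before Amendment 08, so that row has little exposure from baselines above its threshold.
- **That the case mix does differ between cohorts, so that a cohort could look toxic or clean by who entered it.** The documents do not show which cohorts enrolled under which limit, or that any subject had a baseline above 450 ms. The mix may differ. Counting such subjects can only raise a row; it cannot make a cohort look clean.
- **That dose decisions are distorted.** The MTD follows DLT counts, the RP2D rests on an integrated evaluation by the Safety Review Committee, and no rule depends on these rows.

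**Conclusion.** The point holds as a reporting weakness that is cheap to remove. The >450 ms row can count stable pre-existing prolongation as a post-baseline abnormality, as can the >480 ms row, mainly for subjects enrolled before Amendment 08. Both can therefore overstate on-treatment onset, and the error runs upward only.

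The size per affected subject is exact: 33.3, 16.7 or 2.5 points for groups of 3, 6 or 40. The total size is unknown, because the documents do not give the number of subjects with baseline QTcF above 450 ms. The probabilities and the 5-20% illustration rest on the assumptions stated with them. The primary endpoint is not mis-measured as a whole, since change from baseline is analysed directly.

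**What to change.** In SAP 5.6.5, and for consistency in Protocol 9.7.1.8.5, keep the all-subject counts and add one table of baseline QTcF category (≤450, 451-480, 481-500, >500 ms) by maximum post-baseline category, using the baseline definition in SAP section 8. From it, report newly >450, newly >480 and newly >500 ms counts, each among subjects at or below that threshold at baseline. No signal is lost: a move from 470 to 490 ms appears as newly >480 ms.

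The cost is SAP wording and one extra table from data already collected. Denominators will differ by threshold, which a footnote can explain.

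The table will not remove chance crossings. Under the assumptions in the working, a stable subject with a true value of 445 ms still exceeds 450 ms at least once with probability 0.49-1.00, so the newly >450 ms count should be read alongside the change rows.

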#### 5.6.6 Other Safety Analyses

ECOG performance status will be summarized by visit. Shift tables will present changes from baseline in ECOG performance status to worst post-baseline visit.

Ophthalmologic examination will be summarized for left eye and right eye by visual acuity test and central corneal thickness as continuous variables, and by funduscopic examination and slit-lamp examination in terms of normality (normal/abnormal) and clinically significant at each visit..

Listings of ECOG, MUGA/echocardiogram, and ophthalmologic examinations will be provided.

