7.1.1.2 Clinical Experience with H3B-6527

The current study represents the first clinical investigation of H3B-6527.

7.1.1.3 Common Serious Adverse Events Expected to Occur in the Study Population in the Absence of Study Drug Exposure

Common serious adverse events (SAEs) expected to occur in this study population include hepatobiliary dysfunction, ascites, gastrointestinal hemorrhage, fatigue, abdominal pain and renal failure. The current study represents the first clinical investigation of H3B-6527; therefore, the clinical safety profile of this investigational agent is unknown. Based on nonclinical studies, AEs potentially associated with H3B-6527 may include corneal atrophy, hepatocellular hypertrophy, hepatobiliary toxicity, gastrointestinal toxicity, and focal mineralization with associated hyperphosphatemia. Additional details can be found in the Investigator's Brochure.

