9.3.2 Exclusion Criteria

Subjects who meet any of the following criteria will be excluded from this study:

1. Other malignancy active within the previous 2 years except for basal or squamous cell skin cancer, stage 1 prostate cancer, superficial bladder cancer, or carcinoma in situ of the cervix or breast that has completed curative therapy.
2. Current evidence of corneal disorder/keratopathy including but not limited to corneal epithelial thinning, bullous/band keratopathy, corneal abrasion, inflammation/ulceration, or keratoconjunctivitis (to be confirmed by ophthalmological examination). Pre-existing cataract is not a reason for exclusion.
3. Brain or subdural metastases are not eligible, unless they have completed local therapy and have discontinued the use of corticosteroids for this indication for at least 4 weeks before starting treatment in this study. Any signs (eg, radiologic) or symptoms of brain metastases must be stable for at least 4 weeks before starting study treatment.
4. Genetic diseases of the liver that may complicate review of safety data.
5. Known human immunodeficiency virus infection.
6. Uncontrolled significant active infections, except HBV or HCV. Subjects with HBV are eligible, but should be taking appropriate antiviral medication if indicated. Subjects with HCV are eligible but must not be taking any concomitant treatment for HCV while receiving H3B-6527.
7. Major surgery or other locoregional treatment within 4 weeks before the first dose of study drug or radionuclide treatment (eg, ⁹⁰Yttrium intra-arterial treatment) within 8 weeks before the first dose of drug administration.
8. Inability to take oral medication, or presence of malabsorption syndrome or any other uncontrolled gastrointestinal condition (eg, nausea, diarrhea, or vomiting) that might impair the bioavailability of H3B-6527. Subjects with prior gastric resection are eligible.
9. Use of any drug that is a strong inhibitor or inducer of the CYP3A4 enzyme or the P-glycoprotein transporter within at least 2 weeks before the start of study drug and during the conduct of the study unless there is an emergent or life-threatening medical condition that requires it.
10. Use of any drug known to prolong corrected QT (QTc) interval within at least 2 weeks before the start of the study drug and during the conduct of the study.

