#### 5.6.4 Vital Signs

Descriptive statistics for vital sign parameters (i.e. systolic and diastolic blood pressure, heart rate, respiratory rate, temperature, and weight) and changes from baseline will be summarized over time.

A listing of vital sign measurements will be provided.

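### SAP 5.6.6 summarises eye findings without change from baseline, shift or worst value, so its tables can mask subclinical corneal thinning and new slit-lamp findings

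*SAP*

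**What the plan says.** Protocol 7.1.1.3, drawing on nonclinical studies, states that "AEs potentially associated with H3B-6527 may include corneal atrophy", among other effects. Protocol 9.5.1.4.5 requires visual acuity, funduscopy, slit-lamp and anterior-eye OCT, with central corneal thickness entered on the case report form. Under Tables 6 and 7 these are done at Screening, C1 Day 8, Day 1 of C2 to C6, and off treatment. After C6, Part 2 repeats the ophthalmic examination every other cycle; in Part 1 only OCT is required on that schedule.

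SAP 5.6.6 gives the analysis. For acuity and thickness: "Ophthalmologic examination will be summarized for left eye and right eye by visual acuity test and central corneal thickness as continuous variables". For the other two examinations: "by funduscopic examination and slit-lamp examination in terms of normality (normal/abnormal) and clinically significant at each visit". It adds: "Listings of ECOG, MUGA/echocardiogram, and ophthalmologic examinations will be provided".

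Other safety data are treated differently:

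- Vital signs (SAP 5.6.4): descriptive statistics "and changes from baseline will be summarized over time".
- Laboratory values (SAP 5.6.3): change from baseline by visit and to end of treatment, and shifts to the maximum CTCAE grade.
- ECG (SAP 5.6.5): changes, categories of QTc increase, and shift tables.
- ECOG (SAP 5.6.6, in the paragraph before the eye data): "Shift tables will present changes from baseline in ECOG performance status to worst post-baseline visit".

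SAP 5.3.5 applies no imputation. Protocol 9.3.2 excludes current corneal disorder, but "Pre-existing cataract is not a reason for exclusion".

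**The concern.** Corneal thinning is a change within an eye. A table of thickness values by visit compares different groups of subjects as people leave. The protocol puts the maximum estimated time on treatment at about 4 months (section 9.1.2.4), so later columns may describe a smaller, selected group. A fall in mean thickness can then be diluted, or imitated, by who is still being examined.

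The slit-lamp count has a related weakness. A subject who enters with a cataract can be abnormal at baseline, and a new corneal finding in that eye leaves the normal/abnormal count unchanged.

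The stake is the aggregate safety description of a named risk. Protocol 9.4.4.1 allows cumulative toxicity seen after Cycle 1 to refine the RP2D, and slow subclinical thinning would be an effect of that kind.

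**Working it through.** The plan states no figure for this point, so there is none to reproduce. The documents give 40 subjects per expansion schedule (SAP 4). They give no thickness SD, within-eye correlation, dropout rate or cataract prevalence. Those are assumptions below.

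**1. Noise when the later visit has fewer subjects.** Assume 40 subjects at baseline, m of them at a later visit, the same SD at both visits, and within-eye correlation r. In SD units:

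- Visit mean minus baseline mean: SE = sqrt(1/m + 1/40 − 2r/40)
- Paired change in the m subjects: SE = sqrt(2(1 − r)/m)

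| m | r | Difference in visit means | Paired change | Ratio |
|---|---|---|---|---|
| 15 | 0.80 | 0.227 | 0.163 | 1.4 |
| 15 | 0.90 | 0.216 | 0.115 | 1.9 |
| 15 | 0.95 | 0.210 | 0.082 | 2.6 |
| 30 | 0.90 | 0.115 | 0.082 | 1.4 |
| 38 | 0.90 | 0.079 | 0.073 | 1.1 |

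At m = 40 both formulas become sqrt(2(1 − r)/40), so the ratio is exactly 1.

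**2. Full retention.** The difference in means then equals the mean paired change, but visit-wise summaries give only the SD of the values, not the SD of the change. Reading the two means as unpaired gives SE = SD × sqrt(2/40), which is 5.6 to 7.8 µm for an assumed SD of 25 to 35 µm. The paired SE is SD × sqrt(2(1 − r)/40), which is 0.8 to 3.5 µm for r from 0.98 to 0.80.

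**3. Selective dropout.** This is a simulation of 10,000 trials with n = 40. Assumed values are baseline 540 µm, between-subject SD 35 and measurement SD 8. Everyone attends one early visit, by which time thinning is already present. Dropout before the late visit is given as thinning subjects/others.

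| Scenario | True mean change (µm) | Dropout | Late minus baseline mean (SD) | Trials showing no fall | Mean paired change (SD) | Subjects with worst thinning of 5% or more |
|---|---|---|---|---|---|---|
| 20% thin by 50 µm | 0.2 × −50 = −10 | 50%/50% | −9.9 (7.5) | 9% | −10.0 (5.2) | 21% |
| 20% thin by 50 µm | −10 | 80%/50% | −4.5 (7.7) | 27% | −4.5 (4.4) | 21% |
| 10% thin by 30 µm | 0.1 × −30 = −3 | 80%/50% | −1.3 (6.5) | 42% | −1.3 (3.1) | 7% |

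The paired mean is less noisy but equally biased when thinning subjects leave more often. The worst post-baseline value keeps them, provided they had an examination before leaving. The 5% cut is illustrative only and not a proposed clinical limit.

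**4. Slit-lamp counts.** If a share p is abnormal at baseline and new findings arise independently with probability q, the proportion abnormal later is p + (1 − p)q. The rise is (1 − p)q, so a share p of new findings adds nothing. For p = 0.3 and q = 0.2, the count rises from 0.30 to 0.44, a rise of 0.14 against 0.20 with a new finding. Dropout can flatten it further: 12 of 40 at baseline and 6 of 20 later are both 30%, whether the six are old or new.

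**The case against.** The strongest reply is that the summary tables are not the only output. Four parts of it stand.

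- By-subject ophthalmologic listings are promised in the same section. In Part 1, where planned cohorts are 3 to 6 subjects, individual courses can be read from them.
- Protocol 9.5.1.4.5 makes clinically significant OCT changes adverse events, and also records changes from pretreatment examination that meet the AE definition. Protocol 9.5.1.4.1 defines that broadly, with no general clinical-significance filter. The treatment-emergent definition in SAP 5.6.2 separates new or worsened events from old ones.
- Current corneal disorder, including epithelial thinning, is excluded at entry. The clinical-significance category partly separates an incidental cataract from an important new finding.
- The plan does not give every other safety measure a change analysis: MUGA/echocardiogram gets only a listing. Ophthalmic measures are also not named in the primary safety endpoint, as laboratory values, ECG and vital signs are.

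It can also be said that table shells and derivations sit in separate documents (SAP 9 and 11). Those may add a change column, but the SAP does not commit to one, and it writes change or shift out where it wants it for the four domains above.

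These points limit the concern without removing it. The AE route for OCT depends on site judgement, and the protocol gives no thickness criterion. Listings leave the reader to derive each change by hand, for up to 40 subjects per schedule in Part 2.

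**Conclusion.** The point holds for the summary tables. SAP 5.6.6 names no change from baseline, shift or worst post-baseline value for any eye measure. Its tables can therefore mask thinning that no site judges clinically significant, and new slit-lamp findings in subjects already abnormal at baseline.

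A reader might infer that thinning and new lesions would be hidden altogether, or that the trial could not answer the corneal question. The documents do not support that, because listings are planned and adverse event reporting separates new from old events. Nor do they show that the eye is the most intensively monitored organ: blood chemistry is drawn at more visits, and Part 1 has Holter monitoring.

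The size rests on assumptions. The ratio of 1.4 to 2.6 needs 15 of 40 retained and r of 0.8 to 0.95. At r = 0.9 it is about 1.4 with 30 retained and 1.1 with 38. No inferential test is planned, so this measures how hard the descriptive tables are to read, not a loss of power. Mean change alone does not cure selective dropout; the worst-value and shift tables carry most of the gain. The change should be made, as a low-cost improvement in safety reporting.

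**What to change.** In SAP 5.6.6 add, per eye and with the number examined at each visit:

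1. Change and percent change from baseline in central corneal thickness, and change from baseline in visual acuity, by visit and at end of treatment.
2. Each subject's worst post-baseline change in central corneal thickness.
3. Shift tables from baseline to worst post-baseline for slit-lamp and for funduscopy, using the three levels the SAP already applies to ECG interpretation: normal; abnormal, not clinically significant; abnormal, clinically significant.

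Use the baseline definition in SAP 8. The cost is a few extra columns and the shift tables, programmed from data already collected. No extra visit, new data or protocol amendment is needed, and no clinical rule changes.
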